## Synopsis

The use of monoclonal antibodies either alone or as part of chemoimmunotherapy in oncology, benign and malignant hematology is expanding. Each year, United States Food and Drug administration (FDA) approves new agents or expands the indications of already approved agents. Of the 17 therapeutic monoclonal antibodies approved in 2017, 50% of them are indicated for hematologic and oncologic condition. With increasing number of approved agents and expansion of indications of existing agents, therapeutic monoclonal antibodies have become one of the fastest growing areas in the management of benign and malignant hematologic condition. With advancement of recombinant technology, newer agents are either partially or fully humanized. Despite this, they still carry significant risk of immune and non-immune mediated adverse events. Most of the therapeutic monoclonal antibody related adverse events (MCAAE) are either anaphylaxis or standard infusion reactions.

The severity of reaction is variable, ranging from mild involvement of single organ to severe and life-threatening reactions requiring hospitalization or even resulting in death. In a majority of patients, re-initiation of infusion following resolution of symptoms with or without additional medical intervention is possible.

Even for mild infusion reactions, where re-initiation of infusion is possible, there is resultant delay in delivery of infusions, distress to patients, and additional utilization of health care resources.

Due to unpredictability of standard infusion reaction, efforts have been focused on premedication to decreasing the incidence and severity of infusion reaction. Most institutions have protocols using corticosteroid, acetaminophen and antihistamine as part of their premedication protocols. This has reduced but not eliminated standard infusion reactions. Most recently, mast cell stabilizers are being added to standard protocols to further reduce the incidence and severity of standard infusion reactions with variable anecdotal success without formal study. Of all the monoclonal antibodies, only Daratumumab has been evaluated using this strategy.

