## Hypothesis

We postulate that 10 mg of Montelukast, when given at least 1 hour prior to infusion monoclonal antibodies in addition to standard premedication, will lead to at least 50% decrease in incidence of monoclonal antibody associated Standard Infusion Reactions compared to historic data. It will also lead to shorter infusion time and decrease use of additional health care resources (ER, hospitalization and discontinuation of infusion) and hence better tolerability of infusions.

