## **Background/Significance**

Immunoglobulin molecules (antibodies) are multifunctional components of immune system produced by B-lymphocytes to facilitate cellular and humoral reaction to host and foreign antigens. Most antibodies are produced, as part of immune response, by diverse clones of B-lymphocytes to antigens. They are polyclonal and target portions of antigens that induced their response. Immunoglobulins can also be monoclonal i.e. produced by single clone of B lymphocyte against a specific antigen.

Monoclonal antibodies are produced commercially using recombinant technologies; they have been available in clinical use since 1985. Since revision of naming convention of therapeutic monoclonal antibodies in 2017, over 500 monoclonal antibodies have been registered(1). In 2017 alone, 17 therapeutic monoclonal antibodies are approved by Food and Drug Administration (FDA), of which 8 are indicated for hematologic and oncologic malignancy(2).

In hematology and oncology, monoclonal antibodies are either used alone or in combination with conventional chemotherapy for management of various benign or malignant conditions. Despite high clinical benefit, their drawback has been their unpredictable adverse effects (infusion reactions). For this reason, newer generations of monoclonal antibodies are either partially or fully humanized. Despite this innovation, their use still carries variable risk of infusion reaction depending on the agent, clinical indication and clinicopathologic characteristic of individual being treated.

Monoclonal antibody associated infusion reactions are generally divided into four general types; type 1 like reaction (most common), cytokine- release syndrome, mixed reaction and type IV reaction (least common) (3). For practical purpose, the above are grouped into anaphylaxis infusion reactions (AIRs) and standard infusion reactions (SIRs).

AIRs are mediated by IgE and result in explosive reaction with initial or subsequent exposure. Re-challenge is generally not recommended.

SIRs are mediated by antigen and antibody interaction (human antihuman or human anti-chimeric) or cytokine released from mast cell and monocyte- macrophage systems. The rate and severity of this type can be mitigated by premedication.

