The incidence rates of SIRs are highly variable ranging from 50-80% in Rituximab and Alemtuzumab to 20-30% in Trastuzumab and Cetuximab (4, 5). Incidence is highest with the first and probably the second doses but may recur with subsequent doses in up to 30%(6).

The severities of SIRs are also variable, ranging from mild involvement of single organ to severe reaction resulting in emergency room visit or hospitalization and death. In majority of patients with mild to moderate reactions, re-initiation of therapy with hours to days of break is possible.

Due to unpredictability of SIRs, efforts have been focused on decreasing the incidence and severity of infusion reaction with premedication. Most institutions have adopted various combinations of corticosteroid, acetaminophen and antihistamine as part of their premedication protocols with variable success in reducing the incidence and severity of SIRs.

Despite the above, SIRs still occur with high rates and severities resulting in treatment delays, infusion prolongations, need for additional doses of premedication, emergency room visits and

sometimes hospitalizations. These not only lead to increased cost of treatment but also lasting psychological impact of treatment of patients.

To mitigate the above, efforts are being directed at modifications of premedication or addition of newer agents to further reduce the incidence and severity of SIRs and hence improve tolerability.

Most recently, Montelukast, a mast cell stabilizer has been reported in multiple retrospective and observational studies to either decrease the incidence rate of infusion reactions, shorten infusion time and or decrease the use of additional doses of premedication like corticosteroids whose effect may be counterproductive (7). This has resulted in wide spread use of Montelukast as part of premedication of some monoclonal antibodies without formal study.

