## **Study Methods:**

### *Study design:*

This is a Phase II single arm open label study evaluating 10 mg Montelukast given at least 1 hour prior to infusion of monoclonal antibody in addition to standard premedication. Monoclonal antibodies being evaluated include those commonly used to treat hematologic and oncologic malignancies like (Blinatumomab, Daratumumab, Elotuzumab, Gemtuzumab, Obinutuzumab, and Rituximab).

The study will be introduced to patients who are undergoing treatment with above monoclonal antibody by principal investigator or sub-investigator during routine pre-initiation of immunotherapy or chemoimmunotherapy visits. Patients who are interested in hearing more about the study will be consented to participate in the study. Subjects will then be screened by study coordinator with the PI or Sub-I and those who meet inclusion/exclusion criteria will proceed on the study.

Drug for the study will be dispensed by one of the Research pharmacists affiliated to CCI during routine pretreatment evaluation for patient to take home. The study drug (Montelukast) will be purchased from commercial sources using the funds from the study sponsor. This is an investigator-initiated research with full funding from institutional pilot research grant from the Central California Faculty Medical Group (CCFMG). No additional internal or external funding will be utilized for this study.

Study subjects will be given 10 mg of Montelukast to be orally self-administered at least 1 hour prior to beginning of chemotherapy section. The administration of drug by patient will be verified and documented by inpatient or AIC nurse by history.

If the monoclonal antibody is given more than 3 times weekly, then patient will take Montelukast daily, including at least 1 hour prior to infusion or change of bag.

Standard premedication will be administered according to institution protocol. For details, see the flow chart below in appendix 1.

Rates, ratios and proportions with confidence intervals will be calculated for demographic characteristic and incidence of infusion reactions. McNemar's test will be used to test the differences of average incidence of infusion reaction between first and subsequent infusions.

*Intervention:*

Administration of Montelukast 10 mg at least 1 hour prior to initiation of up to 6 infusion doses/bag changes

*Control:*

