Historic literature and retrospective chart review of patient's treated with above therapeutic monoclonal antibodies from January 2014 to December 2019.

*Covariates:*

History hypersensitivity medications, history of Asthma or Atopy, history of CAD/COPD, Other chemotherapy received by patient during the infusion and tumor burden.

*Study Implementation:*

This study is completely voluntary, and enrolment will not affect the treating oncologist's decision or treatment plan. The study medication, Montelukast, is an FDA approved drug for other indications and is not known to pose serious risk to cancer patient undergoing monoclonal antibody or cancer chemotherapy. Patients will be monitored closely for potential drug-drug interactions during the study period.

Information obtained from patients during the study period will be used solely for study purposes. No additional tissues or samples will be obtained for study purpose other than what is collected or required by treating physician as part of standard of care.

Privacy and confidentiality of patients' information will be protected per CMC guidelines.

Participation of study by subject is voluntary and will not require additional visits other than 24-hour post infusion phone call to complete a study related questionnaire. Study subjects will not be reimbursed for participation.

Study will be conducted over 2 years with an estimated yearly accrual of at least 40 patients per year.

The study will be conducted upon approval of CMC Institutional Review Board IRB and will follow Helsinki declaration and Good Clinical Guideline.

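### The historic control is not tied to the trial's background premedication, so the comparison in the Hypothesis can be biased in either direction by an unknown amount

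*Combined protocol and SAP*

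**What the plan says.** The Hypothesis is comparative: Montelukast on top of standard premedication "will lead to at least 50% decrease in incidence of monoclonal antibody associated Standard Infusion Reactions compared to historic data". Under Study Methods, the Control entry reads "Historic literature and retrospective chart review of patient's treated with above therapeutic monoclonal antibodies from January 2014 to December 2019". It conditions on the antibody and the dates, and on nothing else. The Covariates entry directly below it is "History hypersensitivity medications, history of Asthma or Atopy, history of CAD/COPD, Other chemotherapy received by patient during the infusion and tumor burden". The first item most naturally means past hypersensitivity to medications; none of the five is the corticosteroid, antihistamine or acetaminophen given before the infusion.

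For trial patients the background is fixed: "Standard premedication will be administered according to institution protocol", with details left to Appendix 1. No matching sentence applies to the controls.

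On the importance of premedication the protocol is clear. Background/Significance says of SIRs: "The rate and severity of this type can be mitigated by premedication". The Synopsis says of the usual three-drug premedication: "This has reduced but not eliminated standard infusion reactions". Background/Significance also reports that most institutions use "various combinations of corticosteroid, acetaminophen and antihistamine as part of their premedication protocols with variable success".

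Data Collection names the number of doses used to treat a reaction, which is an outcome and not baseline premedication. It refers to Appendix 2 for the full data plan; that appendix is not in the text available for this review.

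**The concern.** The question is what Montelukast adds to standard premedication. A historic comparison answers it only if the background premedication is alike on both sides. By the protocol's own account, premedication affects the outcome and varies between institutions, so it is a potential confounder of this contrast. As written, the contrast is Montelukast plus current local premedication against whatever was given in the literature series or in local charts over six years.

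If trial patients are premedicated more fully than controls, the reduction is overstated. If they are premedicated less fully, a real effect is hidden. Either would mislead the planning of the Phase 3 trial that Background/Significance says this study is meant to inform.

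**Working it through.** **What can be reproduced.** The only planned figure is enrolment: 2 years x 40 patients per year = 80, which agrees with Sample Size. It rests on resources and availability. No alpha, power or control rate is stated, so there is no further design figure to reproduce.

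**Inputs for an illustration.**
- From the documents: a target relative reduction of at least 50% (Hypothesis), and 80 patients (Sample Size).
- Assumed: SIR rate 50% with full premedication and 75% without; Montelukast has no effect; every trial patient is fully premedicated; a share *f* of controls is. The protocol gives no SIR rates split by premedication. Its 50-80% range in Background/Significance covers Rituximab and Alemtuzumab together, and Alemtuzumab is not a study drug.

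**Formula.** Control rate = *f* x 0.50 + (1 - *f*) x 0.75. Trial rate = 0.50. Apparent reduction = 1 - 0.50 / control rate.

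| Share of controls fully premedicated | Control rate | Apparent reduction with an inert drug |
|---|---|---|
| 100% | 50.0% | 0% |
| 90% | 0.45 + 0.075 = 52.5% | 1 - 0.50/0.525 = 4.8% |
| 80% | 0.40 + 0.15 = 55.0% | 1 - 0.50/0.55 = 9.1% |
| 60% | 0.30 + 0.30 = 60.0% | 1 - 0.50/0.60 = 16.7% |

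**Other direction.** If all controls but only 80% of trial patients were fully premedicated, the trial rate would be 55% against 50%. An inert drug would then appear to raise the rate by 10% (0.55/0.50 = 1.10), and a real benefit would be partly masked.

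**Sensitivity to the assumed strength of premedication.** Let full premedication multiply SIR risk by *r*, and let *p* be the rate without it (50% to 80%). Historic rate = *p*(1 - *f* + *fr*), trial rate = *pr*, apparent reduction = 1 - *r*/(1 - *f* + *fr*). For the chance of a false benefit, take an exact one-sided 2.5% binomial test with 80 patients against the historic rate treated as fixed. The plan specifies no such test; this only gives a scale.

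- *r* = 0.7, *f* = 50%: 1 - 0.70/0.85 = 18%; false-benefit chance 21% (*p* = 50%) to 56% (*p* = 80%).
- *r* = 0.7, *f* = 90%: 1 - 0.70/0.73 = 4%; about 4% to 5%.
- *r* = 0.9, *f* = 90%: 1 - 0.90/0.91 = 1%; about 2% to 3%, so negligible.
- *f* = 100% (same premedication on both sides): 0%; 1.5% to 2.5% in the scenarios run.

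The bias runs from negligible to material, depending on two quantities that the documents do not give.

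**The case against.** The case on the other side has five parts.

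1. **Unseen appendices.** Appendix 1 holds the premedication details and Appendix 2 the data plan. This stands as a limit: one cannot say that premedication goes unrecorded. But recording it would not by itself make it a covariate or a condition for entering the control.

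2. **Local controls.** Chart-review data come from the EPIC record (Confidentiality and Privacy), so these patients may largely have followed the same institutional protocol, and nothing shows that it changed. This stands too, and puts the greater exposure in the literature part. However, the plan neither states that local premedication was the same nor provides for checking it.

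3. **Size.** A reader might infer that most of the hypothesised reduction could arise with an inert drug. On the 50%/75% assumption that needs something like only 20% of controls fully premedicated: control rate 0.10 + 0.60 = 70%, apparent reduction 1 - 0.50/0.70 = 29%. This fits poorly with the protocol's statement that most institutions already premedicate, and the 50%/75% split is itself an assumption. The documents do not support that inference.

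4. **Reach.** The primary objective and endpoint report incidence in one arm, and Background/Significance calls the study a hypothesis-generating pilot. The primary estimate is indeed unaffected. The Aim, the Hypothesis and the named Control are nevertheless comparative.

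5. **Remedy.** Statistical Analysis contains no comparison with the control and no model, so adding a covariate alone would change nothing. This is correct, and the fix must reach that section.

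**Conclusion.** The concern holds in limited form. The control has no premedication condition and the covariate list omits premedication, although the protocol treats it as affecting SIR rates and varying between institutions. The comparison in the Hypothesis can therefore be biased either way.

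The size is unknown. About 5%, 9% and 17% apparent reduction (at 90%, 80% and 60% of controls fully premedicated) are illustrations. They rest on the assumed 50% and 75% rates, an inert drug and a fully premedicated trial cohort. Against a target of 50%, that is roughly a tenth to a third of the claimed effect (4.8/50 to 16.7/50).

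Two stronger readings are not supported. One is that the trial's incidence estimate is invalid: it involves no control. The other is that the bias could never be measured or removed: the chart review draws on an electronic record from which premedication should be recoverable, and Appendix 2 may already capture it. This should be changed before the comparison is made, but it does not undermine the descriptive result.

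**What to change.** - **Data Collection:** unless Appendix 2 already does so, record for each infusion, in both the trial and the chart review, the corticosteroid, antihistamine and acetaminophen given beforehand, including corticosteroid that belongs to the treatment regimen.
- **Control:** make the main control the chart-review patients who received the institution's standard premedication for that antibody. Use literature rates as context only, since without patient-level data they can be selected but not adjusted.
- **Covariates:** add background premedication.
- **Statistical Analysis:** state that the comparison with this control is made by antibody with premedication accounted for. Report the unrestricted chart-review comparison as a sensitivity analysis.

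The cost is extra abstraction: up to 6 x 80 = 480 trial infusions plus those of the controls, from a record already being searched. The control group will also be smaller, and with six antibodies some groups may be very small; the sensitivity analysis is there for that reason. No patient's treatment changes.

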**Data Collection:**

Demographic and clinical data will be collected according to the study plan (Appendix 2). Infusions will be administered per standard of care. The study investigators will obtain information about time of onset, time of completion, types and degree of infusion reaction(s), number of doses of additional medication used to treat infusion reaction and post infusion disposition locations. National Cancer Institute Common Terminology of Standard Adverse Effect (NCI CTCAE v5.0) will be used to grade Infusion-related reactions and Immune system disorder as shown in appendix 4.

Follow up phone calls to patients by study coordinator to ascertain additional reactions and treatments received will be documented. Patients will complete the study on completing 6th dose/bag change of infusion or progression of disease or change of therapy, whichever comes first. For patients on continuous infusion, change of bag will be used as reference point.

## **Measured Outcomes:**

### *Primary endpoint*

1. To estimate the incidence rate of SIRs during above monoclonal antibody infusions.

### *Secondary endpoints*

1. To estimate the average infusion duration of the above monoclonal antibodies
2. To estimate the incidence of Grade 3 or more monoclonal antibody infusion reaction
3. To estimate the rate of discontinuation of monoclonal antibody infusion due to SIRs

## **Risks of Study Medication:**

Risks and side effects related to Singulair include those which are:

### Likely adverse reactions (above 5%):

- Upper respiratory infection
- Fever
- Headache
- Pharyngitis (inflammation of the back of the throat)
- Cough
- Abdominal pain
- Diarrhea
- Otitis Media (middle ear infection)
- Influenza
- Rhinorrhea (runny nose)
- Sinusitis (inflammation or swelling of the tissue lining the sinuses)
- Otitis (ear infection)

### Less Likely adverse reactions (more than 1% to 5%):

- Fatigue
- Dyspepsia (indigestion)
- Dental pain
- Gastroenteritis (stomach flu)
- Dizziness
- Rash
- Increase in ALT/AST (blood tests evaluating your liver)
- Pyuria (increase in number of white blood cells in the urine)

### Very rare but serious adverse reactions (less than 1%):

- Neuropsychiatric events (see below)
- Eosinophilic conditions (see below)

*Neuropsychiatric events:* Neuropsychiatric events have been reported in adult, adolescent, and pediatric patients taking Singulair. Post-marketing reports with Singulair use include, but are not limited to, agitation, aggressive behavior or hostility, anxiousness, depression, disorientation, disturbance in attention, dream abnormalities, dysphemia (stuttering), hallucinations, insomnia,

irritability, memory impairment, obsessive compulsive symptoms, restlessness, somnambulism, suicidal thinking and behavior (including suicide), tic, and tremor. The clinical details of some post-marketing reports involving Singulair appear consistent with a drug-induced effect.

*Eosinophilic conditions:* Patients with asthma on therapy with Singulair may present with systemic eosinophilia, sometimes presenting with clinical features of vasculitis consistent with Churg-Strauss syndrome, a condition which is often treated with systemic corticosteroid therapy. These events have been sometimes associated with the reduction of oral corticosteroid therapy.

*Other precautions:*

- Aspirin sensitivity: Patients with known aspirin sensitivity should continue avoidance of aspirin or non-steroidal anti-inflammatory agents while taking Singulair. Although Singulair is effective in improving airway function in asthmatics with documented aspirin sensitivity, it has not been shown to truncate bronchoconstrictor response to aspirin and other non-steroidal anti-inflammatory drugs in aspirin-sensitive asthmatic patients.
- Phenylketonuria: Phenylketonuria patients should be informed that the 4-mg and 5-mg chewable tablets contain phenylalanine (a component of aspartame), 0.674 and 0.842 mg per 4-mg and 5-mg chewable tablet, respectively.

